4.2 General Guidelines

4.2.1 Prior to Consent

Prior to consenting a patient, site staff must verify a slot is available by checking either the PBTC Protocol Status web page or using the CTSU OPEN Slot Reservation System.

4.3 Enrollment Procedures

The Oncology Patient Enrollment Network (OPEN) is a web-based registration system available on a 24/7 basis. OPEN is integrated with CTSU regulatory and roster data and with the PBTC registration/randomization systems for retrieval of patient registration/randomization assignment. OPEN will populate the patient enrollment data in NCI's clinical data management system, Medidata Rave.

Requirements for OPEN access:

- A valid CTEP-IAM account;
- To perform enrollments or request slot reservations: Must be on an PBTC roster with the role of Registrar. Registrars must hold a minimum of an Associate Plus (AP) registration type;
- The registrars must hold the OPEN Registrar task on the DTL for the site; and
- Have an approved site registration for the protocol prior to patient enrollment.

To assign an Investigator (IVR) or Non-Physician Investigator (NPIVR) as the treating, crediting, consenting, drug shipment (IVR only), or receiving investigator for a patient transfer in OPEN, the IVR or NPIVR must list the IRB number used on the site's IRB approval on their Form FDA 1572 in RCR. The IVR or NPIVR must be assigned the appropriate OPEN-related tasks on the DTL.

Prior to accessing OPEN, site staff should verify the following:

- Patient has met all eligibility criteria within the protocol stated timeframes; and
- All patients have signed an appropriate consent form and HIPAA authorization form (if applicable).

Note: The OPEN system will provide the site with a printable confirmation of registration and treatment information. You may print this confirmation for your records.

Access OPEN at <https://open.ctsu.org> or from the OPEN link on the CTSU members' website. Further instructional information is in the OPEN section of the CTSU website at <https://www.ctsu.org> or <https://open.ctsu.org>. For any additional questions, contact the CTSU Help Desk at [name] or [REDACTED].

Patient enrollment for this study will be facilitated using the Slot Reservation System in conjunction with the registration system in OPEN. Prior to discussing protocol entry with the patient, all site staff must use the CTSU OPEN Slot Reservation System to ensure that a slot on the protocol is available to the patient. Once a slot reservation confirmation is obtained, site staff may then proceed to enroll the patient to this study.

5 Treatment Plan

Treatment may be administered on an outpatient basis. Reported adverse events and potential risks are described in Section 7. Appropriate dose modifications are described in Section 6. No investigational or commercial agents or therapies other than those described below may be administered with the intent to treat the patient's tumor.

5.1 *Agent Administration*

Patients with recurrent/progressive DIPG will be enrolled at the time of progression in Stratum 1. Therapy with panobinostat will be administered every other day, 3 times/ week, p.o. preferably on a Monday/Wednesday/Friday schedule for three weeks, followed by one week off of therapy. Three weeks of therapy plus the one week rest period (total 4 weeks) will constitute one course. Treatment will continue for up to 26 courses (approximately 2 years) barring progressive disease or unacceptable toxicity.

Patients with DIPG or H3K27M+ Thalamic DMG who have not progressed will be enrolled after receiving standard radiation therapy in stratum 2 and cannot begin treatment until at least 14 days after completion of radiation. Therapy with panobinostat will be administered every other day, 3 times/ week, every other week. **A minimum of 6 days without drug is required between treatment weeks.** Four weeks will constitute one course. Treatment will continue for up to 26 courses (approximately 2 years) barring progressive disease or unacceptable toxicity.

5.1.1 *Panobinostat*

Panobinostat will be provided by Secura Bio Inc. Oral panobinostat will be supplied as 5 mg, 10 mg, 15 mg orange colored, and/or 20 mg reddish colored opaque, hard gelatin capsules.

Subjects will be assigned a dose level at the time of enrollment. See Section 5.1.6 below for details of dose escalation schedule. See Section 6 for dose modifications.

Dosing should be adjusted based on BSA calculated at the beginning of each course of therapy. The dose prescribed should be rounded to the nearest deliverable dose based on the BSA adjustment and the available pill sizes. Dosing Tables which reflect this approach are available in **Appendix D: Dosing Tables**. Patients will be provided with a Medication Diary for panobinostat, instructed in its use, and asked to bring the diary as well as the remaining pill bottles with them to each appointment. The Patient Diary is available in

Appendix E: Patient Diary.

Patients are encouraged to take their dose of panobinostat at the same time each day, preferably in the morning. Each dose of panobinostat should be taken with a 4 oz / 120 ml glass of water. Drug must be taken on an empty stomach (either 1 hour before or after meals) on Course 1, Days 1 and 3, and may be taken with or without food for the remaining doses. Patients should be instructed to swallow the capsules whole and not chew them. Patients must avoid grapefruit or grapefruit juice and Seville (sour) oranges during the entire study.

If the patient forgets to take his/her dose during the morning on a scheduled treatment day, then he/she should take panobinostat on that same day within 12 hours after the missed dose if possible. After more than 12 hours, that day's dose should be withheld, and the patient should wait to take panobinostat until the next scheduled treatment day (i.e., patients should be instructed not to try to make-up the missed dose after 12 hours). The patient should then continue treatment with the original dosing schedule. If vomiting occurs within 15 minutes, the dose should be repeated. If a dose is missed/ unable to be given, record on the patient diary and continue counting the days of the course, with treatment administered on originally scheduled days.

5.1.2 Criteria for Starting Subsequent Courses

A course may be repeated every 28 days if the patient has at least stable disease, has not met any off treatment criteria (Section 5.3.2), has again met laboratory parameters as defined in Section 3.1.7, and any significant toxicity has resolved to acceptable parameters as indicated in Section 6.

5.1.3 Dose-Limiting Toxicity

Management and dose modifications associated with adverse events are outlined in Section 6. DLT will be defined as any of the events listed in this section that are at least possibly related to panobinostat that occur during the dose-finding period regardless of expectedness. The dose-finding period is defined as the first course of therapy in both strata.

Management and dose modifications for toxicities which occur outside of the dose-finding period should also follow Section 6; however, these will not be considered dose limiting for the purpose of dose escalation.

5.1.4 Definitions of Dose-Limiting Toxicities (DLTs):

Patients who miss more than 2 doses due to toxicity will be considered to have experienced a DLT.

5.1.4.1 Non-hematologic dose limiting toxicity is defined as:

- Any Grade 3 or greater non-hematologic toxicities with the specific exclusion of the following:
 - o Grade 3 nausea/vomiting that is responsive to antiemetics, and that resolves to \leq Grade 2 within 5 days
 - o Grade 3 electrolyte abnormality that resolves to \leq Grade 2 within 5 days
 - o Grade 3 rash that is not considered medically significant or intolerable by the

- patient
 - Grade 3 diarrhea that resolves to \leq Grade 1 with optimal use of anti-diarrheal medication
 - Grade 3 fever that resolves to \leq Grade 2 within 5 days
 - Grade 3 infection that resolves to \leq Grade 2 within 5 days
- Any Grade 2 non-hematological toxicity that persists for more than 7 days and is considered sufficiently medically significant or sufficiently intolerable by patients as to warrant treatment interruption and/or dose reduction will be considered dose limiting.
- Any panobinostat-related non-hematological toxicity that results in a delay of treatment $>$ 14 days between treatment courses

5.1.4.2 *Hematologic dose limiting toxicity is defined as:*

- Grade 4 thrombocytopenia (platelet count $<$ 25,000/ μ L)
- Grade 3 thrombocytopenia with bleeding
- Grade 3 thrombocytopenia (platelet count \geq 25,000 but $<$ 50,000/ μ L) that occurs twice within a treatment course will be considered a DLT. (Note: platelet transfusions are recommended for platelet counts $<$ 50,000/ μ L and transfusion should target platelet corrections to $>$ 100,000 / μ L)
- Myelosuppression that causes greater than a 14-day delay between treatment courses
- Grade 4 neutropenia
- Grade 3 or 4 febrile neutropenia

5.1.4.3 *Follow-up for toxicities:*

Patients whose treatment is interrupted or permanently discontinued due to an adverse event or abnormal laboratory value must be followed until resolution or stabilization of the event, or initiation of another antitumor treatment, or initiation of hospice/symptomatic care only, whichever comes first.

All patients will be followed for adverse events and serious adverse events for at least 30 days following the last dose of oral panobinostat, or upon initiation of another antitumor treatment.

5.1.5 *Dose-finding Period*

The dose finding period begins with the initial dose of panobinostat and ends on the last day of course 1 (approximately 4 weeks). Should there be a delay starting the subsequent course, dose finding will complete on the start date of the subsequent course.

5.1.6 *Dose Escalation Schema*

Enrollment will commence at dose level 1 i.e. 10mg/m². The dose finding will be governed by a two stage continual reassessment method (CRM), as detailed in Section 13 of this protocol. No intra-patient dose escalations will be allowed.

Table 10 below provides the dose escalation schedule proposed for Stratum 1. While the starting dose level is lower than what has been tolerated in the pediatric Phase 1 study in hematologic malignancies, it reflects the dose levels agreed upon by Novartis. Also note that the dose increments are higher than the conventional 30% in the lower doses. This was done in order to avoid overlaps in the deliverable doses due to pill size limitations as applied to BSA based dosing. Please see Section 13.1.1 for further details.

Table 10: Proposed dose escalation schedule for panobinostat in children with recurrent/progressive DIPG (Stratum 1)

Dose level #	panobinostat oral dose (mg)	Minimum BSA Restriction
0*	5 mg/m ² /day MWF, three weeks on, one week off (1 course = 28 days)	Patients must have a BSA $\geq 0.80\text{ m}^2$
1 (starting dose level)	10 mg/m ² /day MWF, three weeks on, one week off, (1 course = 28 days)	Patients must have a BSA $\geq 0.65\text{ m}^2$
2	16 mg/m ² /day MWF, three weeks on, one week off, (1 course = 28 days)	Patients must have a BSA $\geq 0.65\text{ m}^2$
3	22 mg/m ² /day MWF, three weeks on, one week off, (1 course = 28 days)	Patients must have a BSA $\geq 0.65\text{ m}^2$
4	28 mg/m ² /day MWF, three weeks on, one week off, (1 course = 28 days)	Patients must have a BSA $\geq 0.50\text{ m}^2$
5	36 mg/m ² /day MWF, three weeks on, one week off, (1 course = 28 days)	Patients must have a BSA $\geq 0.50\text{ m}^2$
	Panobinostat will be administered as a single agent * Dose level 0 represents a potential treatment dose for patients requiring a dose reduction from dose level 1 and may be used as a contingency dose level if the starting dose level of panobinostat is not tolerated in the initial cohort.	

Upon completion of Stratum 1, patients with DIPG who have received adequate radiation therapy but have not yet progressed will be enrolled in Stratum 2. Panobinostat will be administered every other day, 3 times/week, every other week p.o. preferably on a Monday/Wednesday/Friday schedule. Total 4 weeks will constitute one course. Treatment will continue for up to two years (26 courses) unless the patient experiences progressive disease, unacceptable toxicity or any of the off-treatment criteria.

The starting dose (dose level 1) for Stratum 2 will be 1 dose level above the highest safe dose for the '3-weeks on, 1-week off' schedule as determined in Stratum 1. The rationale is that 1 week on

1 week off schedule represents a reduction in the amount of drug patients will receive per course and thus a dose level that is safe for ‘3-weeks on, 1-week off’ schedule should also be safe for the every other week schedule.. The current expectation is that $10\text{mg}/\text{m}^2$ will be the MTD for the ‘3-weeks on, 1-week off’ schedule and thus we expect to start exploring the ‘every other week’ dosing schedule at $16\text{ mg}/\text{m}^2/\text{day}$. However, if $10\text{mg}/\text{m}^2$ dose level is determined to be unsafe in the ‘3-weeks on, 1-week off’ schedule we will abandon that schedule and initiate dose escalation for Stratum 2 at $10\text{mg}/\text{m}^2$. The table below lists the proposed dose levels to be studied:

Table 11

Proposed dose escalation schedule for panobinostat in children with non-progressed DIPG or H3K27M+ Thalamic DMG (Stratum 2)

Dose level #	panobinostat oral dose (mg)	Minimum BSA Restriction
-1*	5 $\text{mg}/\text{m}^2/\text{day}$ MWF, every other week (1 course = 28 days)	Patients must have a BSA $\geq 0.80\text{ m}^2$
0*	10 $\text{mg}/\text{m}^2/\text{day}$ MWF, every other week (1 course = 28 days)	Patients must have a BSA $\geq 0.65\text{ m}^2$
1	16 $\text{mg}/\text{m}^2/\text{day}$ MWF, every other week (1 course = 28 days)	Patients must have a BSA $\geq 0.65\text{ m}^2$
2	22 $\text{mg}/\text{m}^2/\text{day}$ MWF, every other week (1 course = 28 days)	Patients must have a BSA $\geq 0.65\text{ m}^2$
3	28 $\text{mg}/\text{m}^2/\text{day}$ MWF, every other week (1 course = 28 days)	Patients must have a BSA $\geq 0.50\text{ m}^2$
4	36 $\text{mg}/\text{m}^2/\text{day}$ MWF, every other week (1 course = 28 days)	Patients must have a BSA $\geq 0.50\text{ m}^2$
	Panobinostat will be administered as a single agent * Dose levels 0 and -1 represent potential treatment doses for patients requiring a dose reduction from dose level 1 and may be used as a contingency dose level if the starting dose level of panobinostat is not tolerated in the initial cohort.	

If patients are unable to tolerate the protocol-specified dosing schedule, dose adjustments are permitted in order to keep the patient on study drug. If administration of panobinostat must be interrupted because of unacceptable toxicity, drug dosing will be interrupted or modified according to Sections 6.2 and 6.3. The first course (day of first dose until initiation of Course 2) will be the DLT observation period.

5.2 Concomitant Medications and Supportive Care Guidelines

5.2.1 Potential QTc prolonging medications

Concomitant medications which can prolong the QTc interval should not be used. Please see **Appendix B: Medications Which May Cause QTc Prolongation**, for a partial list of medications with the potential to prolong the QTc interval. Providers should consult a frequently-updated drug information reference for a complete list.

5.2.2 CYP3A4 and CYP2D6

Co-administration with medications that are strong CYP3A4 inducers should be avoided. Co-administration with medications that are strong CYP3A4 inhibitors and sensitive CYP2D6 substrates is feasible when medically necessary and with close monitoring. Please see **Appendix C: Partial List of Common Moderate and Strong Inhibitors of CYP3A4, and Common Sensitive CYP2D6 Substrates**. Providers should consult a frequently-updated drug information reference for a complete list.

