Panobinostat was FDA approved with a Boxed Warning regarding severe diarrhea. Severe diarrhea occurred in 25% of patients treated with panobinostat. Diarrhea of any grade occurred in 68% of patients treated with panobinostat compared to 42% of patients in the control arm. Diarrhea can occur at any time. Patients must be monitored for hydration status and electrolyte levels, including potassium, magnesium and phosphate.

Panobinostat PK in Combination with Dexamethasone

In clinical studies in multiple myeloma (MM) where panobinostat was given in combination with bortezomib and dexamethasone, the exposure of panobinostat was decreased by 20 to 50% by the concomitant use of dexamethasone (Dex), which is a dose-dependent mild/moderate CYP3A4 inducer. Furthermore, in-silico data showed that the systemic exposure of panobinostat may be decreased by 70% in the presence of strong inducers of CYP3A4. Therefore, it is suggested that the concomitant use of strong CYP3A4 inducers be avoided.

Conclusions on Human Pharmacokinetics and Metabolism

Panobinostat has linear pharmacokinetics at doses of 10-30 mg. Panobinostat can be administered without regard to food. Panobinostat is extensively metabolized and eliminated nearly equally in kidney and liver. Starting dose adjustments are not necessary in patients with severe renal impairment. Starting dose of panobinostat should be reduced in patients with mild and moderate hepatic impairment, and in patients with co-administration of a strong CYP3A inhibitor. Avoid co-administration with medications that are strong CYP3A4 inducers and sensitive CYP2D6 substrates or 2D6 substrates with narrow therapeutic index. Co-administration with medications that are strong CYP3A inducers is to be avoided when combined with panobinostat, bortezomib and dexamethasone⁶⁰.

2.4 *Rationale of Proposed Pediatric Study*

We propose the use of panobinostat to assess safety, tolerability, and pharmacokinetics, as well as initial observations of any clinical effect, in pediatric patients with recurrent/progressive diffuse intrinsic pontine glioma (DIPG). Our rationale is based on pre-clinical evidence including the sensitivity of patient-derived DIPG cell lines to histone deacetylase (HDAC) inhibitors in *in vitro* cell culture studies, and tumor inhibitory effect of panobinostat in *in vivo* efficacy studies performed using orthotopic xenograft models of DIPG.

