2.5.1.2 Preclinical and Clinical Data

Because there are limited pediatric pharmacokinetic (PK) studies of this agent and none in this

population, PK information from this study will be essential for evaluating toxicity and disease response and for refining dosing in future clinical trials of panobinostat. Mandatory pharmacokinetic studies are needed to characterize the full PK profile of panobinostat in this patient population, correlate PK with toxicities, and evaluate effects of concomitant medications such as dexamethasone. Insights into the biologically active dosage will be gained by relating panobinostat systemic exposure (e.g., AUC) to results of pharmacodynamic studies.

In vitro studies indicate that panobinostat is a substrate of CYP3A4, and dexamethasone is a known inducer of CYP3A4. Thus, one might expect lower exposures of panobinostat when administered concurrently with dexamethasone. It will be important to therefore correlate pharmacodynamic effects of panobinostat with PK. The pharmacokinetics of panobinostat may be affected by age, body surface area, steroid use or concomitant medications.

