3.2 EXCLUSION CRITERIA FOR CHILDREN WITH RECURRENT/ PROGRESSIVE DIPG (Stratum 1)

3.2.1 Prior Therapy

- Patients who have had > 60 Gy total radiation to the pons (e.g. patients who have received re-irradiation).
- Patients have had prior HDAC, DAC, HSP90 inhibitors for the treatment of their DIPG.
- Patients have had valproic acid within 28 days prior to enrollment.
- Patients have had prior bone marrow transplant.

3.2.2 *Neurological Status*

Patients have significant acute deterioration in neurologic status in 72 hours prior to enrollment, in the opinion of the treating physician.

3.2.3 *Gastrointestinal*

- Patients have impairment of GI function or GI disease that may significantly alter the absorption of panobinostat, for example severe inflammatory bowel disease.
- Patients have diarrhea > CTCAE grade 2.

3.2.4 *Systemic Illness*

Patients have any clinically significant unrelated systemic illness (serious infections or significant cardiac, pulmonary, hepatic or other organ dysfunction), that in the opinion of the investigator would compromise the ability of the patient to tolerate protocol therapy or put them at additional risk for toxicity or would interfere with the study procedures or results.

3.2.5 *Other Malignancy*

Patients have a history of any other malignancy.

3.2.6 *Transfusions*

Patients are known to be refractory to red blood cell or platelet transfusions.

3.2.7 *Concurrent Therapy*

- Patients who are receiving any other anticancer or investigational drug therapy
- Patients who are required to receive any medication which can prolong the QTc interval.
Please see **Appendix B: Medications Which May Cause QTc Prolongation**.

3.2.8 *Breastfeeding*

Female patient is breastfeeding.

3.2.9 *Inability to Participate*

Patients who in the opinion of the investigator are unwilling or unable to return for required follow-up visits or obtain follow-up studies required to assess toxicity to therapy or to adhere to drug administration plan, other study procedures, and study restrictions

3.3 *INCLUSION CRITERIA FOR CHILDREN WITH NON-PROGRESSED DIPG or H3K27M+ Thalamic DMG (Stratum 2)*

3.3.1 *Diagnosis*

Patients with DIPG or H3K27M+thalamic DMG who have not yet progressed by clinical or radiographic criteria.

- Please note: patients with a radiographically typical DIPG, defined as a tumor with a pontine epicenter and diffuse involvement of more than 2/3 of the pons, are eligible without histologic confirmation.

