3.4.4 Systemic Illness

Patients have any clinically significant unrelated systemic illness (serious infections or significant cardiac, pulmonary, hepatic or other organ dysfunction), that in the opinion of the investigator would compromise the ability of the patient to tolerate protocol therapy or put them at additional risk for toxicity or would interfere with the study procedures or results.

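### Section 5.2.2 permits strong CYP3A4 inhibitors with no panobinostat dose stated, and permits sensitive CYP2D6 substrates, against the protocol's own pharmacokinetic conclusion (reduce; avoid)

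*Combined protocol and SAP*

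**What the plan says.** Section 5.2.2 first says that strong CYP3A4 inducers should be avoided. It then says: "Co-administration with medications that are strong CYP3A4 inhibitors and sensitive CYP2D6 substrates is feasible when medically necessary and with close monitoring". It states no panobinostat dose. For the drug names it points to Appendix C and to an outside drug reference.

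The paragraph titled Conclusions on Human Pharmacokinetics and Metabolism, at the end of Section 2.3.3, takes a different line. The starting dose "should be reduced in patients with mild and moderate hepatic impairment, and in patients with co-administration of a strong CYP3A inhibitor". It goes on: "Avoid co-administration with medications that are strong CYP3A4 inducers and sensitive CYP2D6 substrates". Section 2.5.1.2 gives the mechanism: in vitro, "panobinostat is a substrate of CYP3A4".

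The dose a child receives comes from the level assigned at enrolment and from body surface area (BSA). Section 5.1.1: "Dosing should be adjusted based on BSA calculated at the beginning of each course of therapy". Appendix D turns level and BSA into milligrams. Neither refers to concomitant drugs.

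**The concern.** A site cannot follow both statements. Section 5.2.2 carries over the background advice on inducers but not the advice on inhibitors or CYP2D6 substrates, and it gives no reason for the difference. Close monitoring detects harm after a full dose has been given; the background conclusion asks for less drug beforehand.

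The main stake is the exposed child's safety. Section 2.3.3 describes dose-related thrombocytopenia and other haematologic toxicity in adults, and a boxed warning for severe and fatal cardiac events. The second stake is attribution. Under Section 5.1.3 a listed course-1 event at least possibly related to panobinostat is a DLT at the assigned level, whether or not an interacting drug contributed.

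**Working it through.** **1. The two statements side by side.**

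| Drug class | Section 2.3.3 conclusion | Section 5.2.2 |
|---|---|---|
| Strong CYP3A4 inducer | avoid | avoid |
| Strong CYP3A4 inhibitor | reduce starting dose | feasible if medically necessary, closely monitored; no dose |
| Sensitive CYP2D6 substrate | avoid | feasible on the same terms |

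**2. Does any other section supply a reduced dose?**
- Section 5.1.1 and Appendix D: dose from level and BSA only.
- Section 5.1.6: adjustment if the child cannot tolerate the schedule.
- Sections 6.2 and 6.3: action on study-drug toxicity and on QTcF.
- Section 6.1: the study chair is notified before any dose modification; no dose is set.
- Sections 3.2.7 and 3.4.7: these exclude other anticancer or investigational drugs and "Patients who are required to receive any medication which can prolong the QTc interval"; CYP3A4 inhibitors are not named.
- Appendix C: a list that does not separate strong from moderate inhibitors.

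None does. As written, the dose with a strong CYP3A4 inhibitor is the full assigned dose.

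**3. How much is already barred?** Table 22 has 30 entries marked as inhibitors. Less grapefruit juice and star fruit, that is 28 drugs. Five are named in Table 21 (amiodarone, clarithromycin, erythromycin, telithromycin, voriconazole), leaving 28 − 5 = 23 not barred by name. Table 23 has 48 CYP2D6 substrates, 12 of them in Table 21, leaving 36. Section 5.2.1 bars QTc-prolonging drugs as a class, so 5 and 12 are floors. Grapefruit is barred separately (Section 5.1.1).

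**4. Scale: what rise in exposure would matter?** Inputs: Stratum 2 levels of 16, 22 and 28 mg/m² (Table 11); level 3 declared too toxic and de-escalation to level 2 begun (Section 13.2, Update for Version 8); and "Panobinostat has linear pharmacokinetics at doses of 10-30 mg" (Section 2.3.3, adults). If exposure is proportional to dose:
- level 2 to level 3: 28/22 = 1.27;
- level 1 to level 3: 28/16 = 1.75.

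With Appendix D rounding, level 2 to level 3 is:
- BSA 0.65–0.78: 20/15 = 1.33
- BSA 0.79–0.98: 25/20 = 1.25
- BSA 0.99–1.02: 30/20 = 1.50
- BSA 1.03–1.16: 30/25 = 1.20
- lowest over BSA 0.65–2.50: 40/35 = 1.14 (BSA 1.48–1.51); highest: 1.50

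Only for BSA 0.65–1.16 do both doses lie within 10–30 mg. These are thresholds. The documents give no fold effect of an inhibitor to compare with them.

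**5. How unusual is a 1.27-fold difference without an inhibitor?** Section 2.3.3.1 gives an inter-patient CV of exposure of 59% in adults. Assuming a lognormal distribution, σ = √ln(1 + 0.59²) = √0.2987 = 0.547. Then P(exposure > 1.27 × median) = 1 − Φ(ln 1.273/0.547) = 1 − Φ(0.44) ≈ 33%. Rounding alone spreads level 2 from 15/0.78 = 19.2 to 20/0.79 = 25.3 mg/m², a 1.32-fold range.

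**6. Could one DLT close level 2?** Section 13.1.2 stops assignment to a level with 4 or more treated and at least 33% with a DLT. Section 13.2 says six children had already been treated at level 2, so the next is the seventh if all six are evaluable. 2/7 = 28.6% does not meet the rule. It takes 3 DLTs at n = 7 to 9 and 4 at n = 10 to 12.

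**7. What would a one-level cut do?** From 22 to 16 mg/m² in Appendix D, the smallest cut is 30 to 25 mg (17%, BSA 1.41–1.47) and the largest 25 to 15 mg (40%, BSA 1.03–1.09). These offset rises of 30/25 = 1.20-fold and 25/15 = 1.67-fold.

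**The case against.** Section 2.3.3 is background on adult data, and Section 5.2.2 is the operative rule, limited to medical necessity with close monitoring. Other safeguards exist. Section 3.4.4 excludes a serious infection or other illness that the investigator thinks would "put them at additional risk for toxicity or would interfere with the study procedures or results". QTc-prolonging drugs and grapefruit are barred. Course 1 has weekly blood counts and examinations. The study chair must be told before any dose change. Pharmacokinetic sampling is mandatory (Section 9.2), and Section 13.3.1 plans to relate exposure to toxicity and to concomitant medications. Finally, 1.27-fold lies well inside ordinary variation between patients (step 5), so reaching the average level-3 exposure in one child is not in itself a demonstrated harm.

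Most of this stands, and it limits the severity. It does not remove the inconsistency. None of these safeguards sets the lower dose that the protocol's own conclusion asks for. The sampling runs from day 1 to the day-3 pre-dose of course 1, so it would miss an inhibitor started later, and it describes exposure without changing the dose. Wide natural variation makes the threshold a weak signal, but it gives no reason to add an avoidable rise on top.

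**Conclusion.** The inconsistency is real. A child on a strong CYP3A4 inhibitor would receive the full assigned dose where the protocol's own conclusion calls for a reduction. This rests on the text alone. It is a safety matter of minor to moderate severity, with no effect if no child takes such a drug. The 1.27-fold figure (1.14 to 1.50 with rounding) assumes that adult linear pharmacokinetics carry over to children, and it is given only for scale.

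A reader might infer more. The documents do not support the following:
- **That the MTD is biased.** The fold effect and frequency of use are unknown, and dexamethasone acts the other way (Section 2.3.3 reports exposure lower by 20 to 50%).
- **That one inhibitor-related DLT closes level 2 by moving 1/6 to 2/6.** With six already treated, that step is not open to a new child (step 6). One DLT could still move 2/9 to 3/9, but the DLT count is not given.
- **That a temporary cut would be permanent or use up the child's only reduction.** In Section 6.2 the bar on re-escalation and the removal rule attach to reductions for toxicity, and the one-reduction limit sits under haematological toxicity. The text is silent on an interaction cut; it does not forbid a return to dose.
- **That CYP2D6 substrates lead to too high a panobinostat dose.** For these the advice is avoidance, not a lower panobinostat dose.

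**What to change.** - **Sections 5.2.2 and 3.4.7:** avoid strong CYP3A4 inhibitors at enrolment and during course 1. Mark the strong ones in Table 22.
- **If one becomes medically necessary:** hold panobinostat or give a sponsor-specified reduced dose, after notifying the study chair (Section 6.1). Whether one level lower is enough is the sponsor's clinical decision (step 7).
- **Sections 5.1.6 and 6.2:** state that such a cut is not a toxicity reduction, and that returning to the assigned dose after washout is not an intra-patient escalation.
- **CYP2D6 substrates:** change the wording to avoidance, as in Section 2.3.3.
- **Optional:** report the MTD with and without any child who, in course 1, took a strong inhibitor or had doses held or cut for one. This changes no dose decision.

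Section 3.2.7 needs no edit, because Stratum 2 opened on completion of Stratum 1. Section 5.1.4 needs none either: its missed-dose criterion already applies only to doses missed because of toxicity. DLT and evaluability rules stay as they are.

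The cost is a few sentences, a marked table and at most one extra model run. The downside is an occasional delayed start or held dose. Holding one treatment week in Stratum 2 removes 3 of 6 course-1 doses, and under Section 11.1.1 as written a child who stays on treatment remains evaluable at that lower exposure. That is why the optional analysis also flags held or cut doses.
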